9.6.2 Clinical Data Management

All software applications used in the collection of data will be properly validated following standard computer system validation that is compliant with all regulatory requirements. All data, both CRF and external data (eg, laboratory data), will be entered into a clinical system.

9.7 Statistical Methods

All statistical analyses will be performed by the sponsor or designee after the study is completed and the database is locked. Statistical analyses will be performed using SAS

software or other validated statistical software as required. Details of the statistical analyses will be included in a separate statistical analysis plan (SAP).

9.7.1 Statistical and Analytical Plans

The statistical analyses of study data are described in this section. Further details of the analytical plan will be provided in the SAP, which will be finalized before database lock.

9.7.1.1 Study Endpoints

9.7.1.1.1 PRIMARY ENDPOINT

The primary endpoint is:

- Objective response: number of subjects achieving a best objective response of partial or complete response (PR or CR), by up to 24 weeks after all subjects have completed response assessment. Response assessment will be as determined by investigator.

9.7.1.1.2 SECONDARY ENDPOINTS

The secondary endpoints are:

- PFS: defined as the time from the first dose date to the date of disease progression or date of death (whichever occurs first).
- Safety and tolerability: AEs, SAEs, clinical laboratory values, ECG parameters, vital sign measurements, and performance status.
- DOR: defined as the time from the first date of documented PR or CR to the date of disease progression or date of death (whichever occurs first).
- OS: defined as the time from the first dose date to the date of death.

9.7.1.1.3 EXPLORATORY ENDPOINTS

The exploratory endpoints are:

- Exposure of eribulin mesylate.

9.7.1.2 Definitions of Analysis Sets

The **Full Analysis Set** (FAS) will consist of all subjects who receive at least 1 dose of study drug.

The **Safety Analysis Set** (SAS) will consist of all subjects who receive at least 1 dose of study drug.

The **Pharmacokinetic Analysis Set** (PAS) will include subjects who have at least 1 evaluable plasma concentration and sufficient dosing information.

9.7.1.3 Subject Disposition

The number and percentage of subjects who discontinue the study treatment as well as the reason for discontinuation will be summarized.

9.7.1.4 Demographic and Other Baseline Characteristics

Demographic and other baseline characteristics will be summarized using descriptive statistics. Continuous demographic and baseline variables include age, weight, and vital signs; categorical variables include sex, age group, and race.

9.7.1.5 Prior and Concomitant Therapy

All investigator terms for medications recorded in the CRF will be coded to an 11-digit code using the World Health Organization Drug Dictionary (WHO DD) (2017 or current). The number (percentage) of subjects who took prior and concomitant medications will be summarized on the Full Analysis Set by treatment, Anatomical Therapeutic Chemical (ATC) class (ie, anatomical class, therapeutic class), and WHO DD preferred term. Prior medications will be defined as medications that stopped before the first dose of study drug. Concomitant medications will be defined as medications that (1) started before the first dose of study drug and were continuing at the time of the first dose of study drug, or (2) started on or after the date of the first dose of study drug (or, started at the time of or after the first dose of study drug) up to 28 days after the subject's last dose. All medications will be presented in subject data listings.

9.7.1.6 Efficacy Analyses

Efficacy analyses will be performed on the FAS.

9.7.1.6.1 PRIMARY EFFICACY ANALYSIS

The primary analysis will be based on investigator assessments of tumor response.

The primary analysis is to examine the number of responders within each histology subject cohort. Confirmed response (PR or CR) will be used in this analysis. In each of the histology groups of RMS, NRSTS, and EWS, approximately 15 subjects will be enrolled and treated with eribulin mesylate. Data will be monitored on an ongoing basis; depending on evaluation by the investigators and sponsor, if sufficient responses (PRs or CRs) are observed, then this histology type will be recommended for inclusion in the subsequent study. At the latest, the primary analysis will be performed when approximately 15 subjects have completed 24 weeks of response assessments.

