Supportive care will be allowed as per institutional guidelines. Growth factors that support platelet or white blood cell number or function can only be administered in accordance with dose modification guidelines or for culture proven bacteremia or invasive fungal infection. Prophylactic granulocyte colony-stimulating factor should NOT be administered during Cycle 1.

Subjects should not receive any other anticancer therapy (including chemotherapy, radiation therapy, immunotherapy or biologic therapy) or investigational agents while receiving study drug. If these therapies are administered, the subject will be removed from the study.

Assessments

Efficacy Assessments

Tumor response and progression will be evaluated according to RECIST 1.1 criteria. Copies of all scans for tumor assessments will be sent to an imaging core laboratory designated by the sponsor for quality assessment, archiving and potential independent review. Tumor assessment scans will be performed following the guidelines provided by the imaging core laboratory. Decisions concerning treatment discontinuation due to progressive disease will be based on investigator assessment.

Tumor assessments (CT chest, and CT or MRI abdomen, pelvis, and other known or suspected sites or disease) will be performed during screening and then every 6 weeks (within the sixth week) on a fixed schedule from the date of first study drug administration. Magnetic resonance imaging scans may be used instead of CT scans for abdomen and pelvis; however, chest must be assessed using CT. Scans that were performed within the screening window, but before informed consent, may be used if they were acquired consistent with the guidelines provided by the imaging core laboratory. The same method of assessment must be used at all time-points as used at pre-study. Partial and complete responses will be confirmed at least 4 weeks after initial documentation of PR or CR typically on the next consecutive scheduled tumor assessment. After 24 weeks subjects with CR, PR or stable disease (SD) may have imaging decreased to every 9 weeks (within the ninth week).

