8 STUDY OBJECTIVES

8.1 Primary Objective

The primary objectives of the study are:

- To conduct a preliminary assessment of activity of eribulin mesylate in pediatric subjects with relapsed/refractory RMS, NRSTS or EWS to determine whether each cohort warrants further investigation.

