9.3.3 Removal of Subjects From Therapy or Assessment

The investigator may discontinue treating a subject with study treatment or withdraw the subject from the study at any time for safety or administrative reasons. The subject may decide to discontinue study treatment or withdraw from the study at any time for any reason. The reason for discontinuation will be documented. If a subject discontinues study treatment, the subject will enter the Follow-Up Period and complete protocol-specified off-treatment visits, procedures, and survival follow-up unless the subject withdraws consent. The investigator should confirm whether a subject will withdraw from study treatment but agree to continue protocol-specified, off-treatment study visits, procedures, and survival follow-up, or whether the subject will withdraw consent. If a subject withdraws consent, the date will be documented in the source documents. A subject removed from the study for any reason other than toxicity or progression may be replaced.

During the Follow-Up Period, subjects who have discontinued study treatment without progression should have disease assessments as per the Schedule of Assessments from the date of the last assessment until disease progression as per RECIST 1.1 is documented, death or another anticancer therapy is initiated.

All subjects will be followed for survival until death, except where a subject withdraws consent or the sponsor chooses to halt survival follow-up after completion of the primary study analysis.

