9.7.2 Determination of Sample Size

A total of 45 subjects will be enrolled. In each of the histology groups of RMS, NRSTS, and EWS, approximately 15 subjects will be enrolled and treated with eribulin mesylate. The sample size is considered sufficient based on clinical judgment and is not obtained from statistical calculation.

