9.7.3 Interim Analysis

Data will be monitored on an ongoing basis; depending on evaluation by the investigators and sponsor, if sufficient responses (PR or CR) are observed, then this histology type will be recommended for inclusion in the subsequent study.

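### Does the per-histology recommendation need a stated number of responses and a single cutoff date before the plan can be used?

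*Protocol*

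**What the plan says.** Protocol 8.1 gives the primary objective as a preliminary assessment of activity "to determine whether each cohort warrants further investigation". Protocol 9.7.1.6.1 describes the decision in one sentence: "depending on evaluation by the investigators and sponsor, if sufficient responses (PRs or CRs) are observed, then this histology type will be recommended" for the subsequent study. Protocol 9.7.3 and SAP 6 repeat it as the whole of the interim analysis: "if sufficient responses (PR or CR) are observed, then this histology type will be recommended for inclusion in the subsequent study". The synopsis, Protocol 9.1 and SAP 3.2 use the same formula. No current passage adds a count, a rate or a confidence bound. The sample size of about 15 per cohort "is not obtained from statistical calculation" (Protocol 9.7.2), and SAP 5.3.3 treats multiplicity as not applicable. Investigators assess response (Protocol 9.7.1.1.1). Scans go to a core laboratory "for quality assessment, archiving and potential independent review" (Protocol synopsis, Efficacy Assessments).

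On timing, Protocol 9.7 states: "All statistical analyses will be performed by the sponsor or designee after the study is completed and the database is locked". Protocol 9.7.1.6.1 states: "At the latest, the primary analysis will be performed when approximately 15 subjects have completed 24 weeks of response assessments". Protocol 9.7.1.1.1 and SAP 5.1.1 count responses over a window of up to 24 weeks after all subjects have finished response assessment. Protocol 9.3.3 follows subjects for survival until death, except where consent is withdrawn or "the sponsor chooses to halt survival follow-up after completion of the primary study analysis".

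**The concern.** A study run to make a decision would normally say what result leads to which decision. Here the word carrying the rule has no number behind it. The data are open-label and monitored continuously, and the investigators both score the responses and help judge whether there are enough. The bar could be chosen after the counts are seen and could differ between cohorts. With 1 or 2 responders in 15, one reader could say go and another no-go, and neither would be departing from the plan.

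The timing text adds a second doubt. Read literally, Protocol 9.7 holds every analysis until the study ends, whereas 9.7.1.6.1 sets a latest date well before that. It does not say whether its 15 subjects are per cohort or in total. If that date were a hard cut, a first response seen at Week 24 could not yet have the confirmation, at least 28 days later, that SAP 5.4.1 requires, and would not be counted.

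**Working it through.** **Inputs.** Three cohorts of about 15 (Protocol 9.7.2); 3 × 15 = 45, which agrees with the stated total. No null rate, target rate, alpha or power is given, so there is no sample-size calculation to reproduce. The true rates below (5%, 8%, 20%) and the bars (1, 2, 3) are assumptions. The 8% appears in Protocol 7.1.1.3, but for another drug class in Ewing sarcoma.

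**How much the bar matters.** With X responders among n = 15, P(go) = P(X ≥ r). For r = 1 at 5% this is 1 − 0.95^15 = 1 − 0.463 = 0.537. The others follow from the binomial tail.

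| Bar r | 5% | 8% | 20% |
|---|---|---|---|
| 1 | 0.537 | 0.714 | 0.965 |
| 2 | 0.171 | 0.340 | 0.833 |
| 3 | 0.036 | 0.113 | 0.602 |

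For at least one go in three independent cohorts that share one rate, 1 − (1 − P)³ at 5% gives 0.901, 0.430 and 0.105 for bars of 1, 2 and 3.

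**How often the bar would change the answer.** This depends on which bars are in dispute.
- Bars of 1 and 3 disagree when X is 1 or 2: at 5%, 0.366 + 0.135 = 0.501 (0.601 at 8%, 0.363 at 20%).
- Bars of 1 and 2 disagree only when X = 1: 0.366 at 5%, 0.373 at 8%, 0.132 at 20%.

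**What the SAP interval can settle.** The exact 95% intervals from SAP 5.4.1 are 0.2 to 31.9% for 1/15, 1.7 to 40.5% for 2/15 and 4.3 to 48.1% for 3/15. All three cover both 5% and 20%. The interval describes the data; it is not a decision rule.

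**What is already fixed.** Response is investigator-assessed under RECIST 1.1, with confirmation after at least 28 days (SAP 5.4.1). The denominator is every treated subject (SAP 5.2.1, 5.4). Subjects with missing response status are non-responders (SAP 5.3.5). Tables are by histology and overall (SAP 5). Two analysts with the same data at the same cutoff would report the same count, rate and interval for each cohort.

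**Timing, read together.**
1. Protocol 9.3.3 allows survival follow-up to continue after the primary analysis. The general statement in 9.7 therefore cannot govern that analysis.
2. The latest-date sentence in 9.7.1.6.1 closes a paragraph that sets about 15 subjects in each histology group. Per cohort is the natural reading.
3. That same paragraph requires confirmed response, and the endpoint window in 9.7.1.1.1 can be read as leaving time for pending confirmations.
4. For the worst case, suppose the date is a hard cut. A first response at Week 24 is confirmed at Week 28 at the earliest (24 + 4), or Week 33 on the 9-week scan schedule (24 + 9). Let the last m of 15 subjects have response probability 0.20 × (1 − f), where f is the share of first responses that appear at that scan, and let the rest have 0.20. With a bar of 2 and no loss, P(go) = 0.833. For m = 1 it is 0.830 (f = 0.10) or 0.825 (f = 0.25); for m = 3 it is 0.823 or 0.809. The largest fall is 0.833 − 0.809 = 0.024.

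**The case for a change.** The strongest case for a change is that the primary objective is itself a decision, and a decision whose criterion can be chosen afterwards cannot be reproduced. Writing down a minimum count needs no hypothesis test, no extra patients and no loss of early recommendation, because confirmed responses only accumulate. The SAP, where such detail belongs, repeats the protocol phrase instead. Independent review is mentioned only as a possibility, so nothing outside the study team disciplines the judgment.

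Most of this stands as description. The bar is open, and the tables above show that it matters. It does not show that the plan is wrong. There is no stated error rate to break, and 45 is not a miscalculation. The recommendation concerns a later study: it does not stop enrolment, alter treatment or support an efficacy claim. The Amendment 2.0 entries in the revision history mention a trigger of at least one response, which the current text no longer contains. That superseded wording is no contradiction, but it indicates that judgment was chosen over a number when the cohorts were enlarged, rather than left in by oversight. Asking for a number without being able to name one returns the same choice to the sponsor. A fixed count would also raise questions of its own. Cohorts are only approximately 15: at 5% with a bar of 2, P(go) is 0.14 for n = 13 and 0.21 for n = 17. With open-label monitoring, a bar written now might also follow counts already seen.

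On timing, the wording is untidy, and the SAP uses a data cutoff that it never dates. That cutoff appears in the censoring rules for survival and progression, not in the definition of the response count.

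**Conclusion.** The concern describes the documents correctly but does not call for a change. The missing count is a deliberate trade-off in a small descriptive study: flexibility for the sponsor, at the price of a recommendation that outsiders cannot reproduce. The price is real. Moving the bar from 1 to 3 takes P(go) from 0.54 to 0.04 at an assumed 5% rate, and from 0.96 to 0.60 at 20%. It falls on the sponsor's choice of what to study next and leaves every planned estimate intact. Readers should rest on the confirmed count and exact interval for each cohort, and treat the recommendation as judgment.

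The timing texts are a matter of clarity that analysts can resolve from Protocol 9.3.3 and 9.7.1.6.1. Even a hard cut lowers P(go) by no more than 0.024, given a true rate of 20%, a bar of 2, one to three late subjects, and 10 to 25% of first responses at the Week 24 scan. All rates and bars here are assumed, since the documents give none. The three-cohort figures also assume one common rate across histologies.

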5 ETHICS

5.1 Institutional Review Boards/Independent Ethics Committees

The protocol, Informed Consent Form (ICF), and appropriate related documents will be reviewed and approved by an Institutional Review Board (IRB) or Independent Ethics Committee (IEC) constituted and functioning in accordance with ICH E6 (Good Clinical Practice), Section 3, and any local regulations, ie, Federal Regulations, Title 21 CFR Part 56. Any protocol amendment or revision to the ICF will be resubmitted to the IRB/IEC for review and approval, except for changes involving only logistical or administrative aspects of the study (eg, change in CRA[s], change of telephone number[s]). Documentation of IRB/IEC compliance with the ICH E6 and any local regulations regarding constitution and review conduct will be provided to the sponsor.

A signed letter of study approval from the IRB/IEC chairman must be sent to the principal investigator with a copy to the sponsor before study start and the release of any study drug to the site by the sponsor or its designee (ICH E6, Section 4.4). If the IRB/IEC decides to suspend or terminate the study, the investigator will immediately send the notice of study suspension or termination by the IRB/IEC to the sponsor.

Study progress is to be reported to IRB/IECs annually (or as required) by the investigator or sponsor, depending on local regulatory obligations. If the investigator is required to report to the IRB/IEC, he/she will forward a copy to the sponsor at the time of each periodic report. The investigator(s) or the sponsor will submit, depending on local regulations, periodic reports and inform the IRB/IEC of any reportable adverse events (AEs) per ICH guidelines and local IRB/IEC standards of practice. Upon completion of the study, the investigator will provide the IRB/IEC with a brief report of the outcome of the study, if required.

At the end of the study, the sponsor should notify the IRB/IEC and Competent Authority (CA) within 90 days. In the case of early termination/temporary halt of the study, the investigator should notify the IRB/IEC and CA within 15 calendar days, and a detailed written explanation of the reasons for the termination/halt should be given.

The definition for end of the study, as required by certain regulatory agencies, is the time of data cut-off for the final analysis or the time of last subject/last visit, whichever occurs later.

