9 INVESTIGATIONAL PLAN

9.1 Overall Study Design and Plan

E7389-G000-223 is a Phase 2, multicenter, open-label study to conduct a preliminary assessment of the safety and activity of eribulin mesylate in pediatric subjects with relapsed/refractory RMS, NRSTS, or EWS.

Forty-five pediatric subjects, with approximately 15 subjects each with RMS, NRSTS, or EWS, will be enrolled to receive eribulin mesylate as an intravenous (IV) infusion at a dose of 1.4 mg/m² (Recommended Phase 2 Dose [RP2D]) on Days 1 and 8 of each 21-day cycle as determined by the dose finding study ADVL1314 (Eisai Study E7389-A001-113).

Outline

- Pediatric subjects with relapsed/refractory RMS, NRSTS or EWS will be enrolled to receive therapy with eribulin mesylate.
- For each histology type, approximately 15 subjects will be treated. Data will be monitored on an ongoing basis; depending on evaluation by the investigators and sponsor, if sufficient responses (PRs or CRs) are observed, then this histology type will be recommended for inclusion in the subsequent study.
- Subjects will continue study therapy until progression of disease (per RECIST 1.1), intolerable toxicity or withdrawal of consent.

Pre-study Phase:

Day -28 to -1, computed tomography (CT) / magnetic resonance imaging (MRI) scans must be performed within 28 days prior to study drug administration. All clinical and laboratory test results to determine eligibility must be performed within 7 days prior to study drug administration, unless otherwise indicated.

Treatment Phase:

The treatment phase will start on Day 1 of Cycle 1.

Follow-up:

The follow-up period will begin immediately after the End of Treatment visit until death or informed consent is withdrawn, unless the study is terminated by the sponsor. Subjects will be followed for survival approximately every 12 weeks for 1 year and then annually thereafter. As well as follow-up for survival, the annual surveillance will also assess any long term effects of the study treatment.

During the follow-up period, subjects who have gone off study treatment without progression should have tumor assessments every 6 - 12 weeks, at the investigator's discretion, from the date of last tumor assessment until disease progression is documented, death, or initiation of

another anticancer therapy, whichever occurs first, unless the study is terminated by the sponsor. Follow-up data will be required unless consent is withdrawn.

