9.5.1.4 Tumor Assessments

Tumor response and progression will be evaluated according to RECIST 1.1 criteria. Copies of all scans for tumor assessments will be sent to an imaging core laboratory designated by the sponsor. Tumor assessments will be carried out following the guidelines provided by the imaging core laboratory. Decisions concerning treatment discontinuation for PD will be based on investigator assessment.

Tumor assessments (CT chest, and CT or MRI abdomen, pelvis, and other known or suspected sites or disease) will be performed during screening and then every 6 weeks (within the sixth week) on a fixed schedule from the date of first study drug administration. Magnetic resonance imaging (MRI) scans may be used instead of CT scans for abdomen and pelvis; however, chest must be assessed using CT. The same method of assessment must be used at all time-points as used at pre-study. Partial and complete responses will be confirmed at least 4 weeks after initial documentation of PR or CR, typically on the next consecutive scheduled tumor assessment. After 24 weeks subjects with CR, PR or stable disease (SD) may have imaging decreased to every 9 weeks (within the ninth week). A bone scan using whole body bone MRI, ^{99m}m-technetium based bone scans, ¹⁸F-fluorodeoxyglucose (FDG)-PET/CT scans or ¹⁸F-sodium fluoride positron emission tomography [NaF PET] will be performed during screening to establish a baseline (a historical bone scan performed within 6 weeks before study drug administration is acceptable), approximately every 24 weeks (in

conjunction with a scheduled tumor assessment visit), and as clinically indicated. Lesions identified on bone scans should be followed with cross-sectional imaging.

Brain scans will be performed as clinically indicated to assess potential CNS disease and/or metastases. For subjects with a history of protocol-eligible treated brain metastases, a brain scan will be required at screening and all tumor assessment time points (eg, every 6 weeks).

Subjects who discontinue treatment without objective evidence of disease progression will continue to have tumor assessments performed, per the schedule of assessments, until disease progression, death, or initiation of another anticancer therapy.

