5.4.1 Primary Efficacy Analyses

The primary analysis will be based on investigator assessments of tumor response according to RECIST 1.1 ([Eisenhauer, et al. 2009](#)).

The primary analysis is to examine the number of responders (CR or PR) within each histology subject cohort. Confirmed response (PR or CR) will be used in this analysis. All responses must be confirmed no less than 28 days following the initial assessment of response. In order for stable disease (SD) to be considered the best overall response, it must occur ≥ 5 weeks following the first dose of study drug.

Objective response rate (ORR) is defined as the proportion of subjects achieving the best overall response (BOR) of CR or PR as per RECIST 1.1. ORR will be calculated with a 2-sided, exact 95% confidence interval (CI), using the Clopper-Pearson method.

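### Do the protocol's statements on when the primary analysis takes place leave the responder count open?

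*Protocol*

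**What the plan says.** Four places bear on timing.

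- Protocol 9.7: "All statistical analyses will be performed by the sponsor or designee after the study is completed and the database is locked".
- Protocol 9.7.1.6.1, repeated in the synopsis: "At the latest, the primary analysis will be performed when approximately 15 subjects have completed 24 weeks of response assessments".
- Protocol 9.3.3 makes an exception to follow-up until death where "the sponsor chooses to halt survival follow-up after completion of the primary study analysis". Protocol 9.1 sets that follow-up: "Subjects will be followed for survival approximately every 12 weeks for 1 year and then annually thereafter". Protocol 5.1 defines end of study as "the time of data cut-off for the final analysis or the time of last subject/last visit, whichever occurs later".
- Protocol 9.7.1.1.1 and SAP 5.1.1 count best responses of PR or CR "by up to 24 weeks after all subjects have completed response assessment".

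On confirmation, SAP 5.4.1 states: "All responses must be confirmed no less than 28 days following the initial assessment of response". On imaging, Protocol 9.5.1.4 states: "After 24 weeks subjects with CR, PR or stable disease (SD) may have imaging decreased to every 9 weeks (within the ninth week)". The same section says confirmation is typically at the next scheduled assessment, and that tumor assessment off treatment ends at progression, death or new anticancer therapy.

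On who is counted, efficacy is analyzed on the Full Analysis Set, which is everyone given at least one dose. SAP 5.3.5 keeps subjects with missing response status in the denominator as non-responders.

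**The concern.** Read side by side, these statements raise three doubts.

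1. If all analyses wait for study completion, a primary analysis triggered by 24 weeks of assessment cannot come first. Yet Protocol 9.3.3 lets survival follow-up be halted after the primary analysis, so the study may still be open at that point.
2. The trigger does not say whether the 15 subjects are per cohort, or whether a subject who progresses, dies or is lost before Week 24 has completed 24 weeks of assessments. Read literally, a cohort in which most subjects progress early might never reach it.
3. A first response at the Week 24 scan cannot be confirmed for at least 28 days. It would be unconfirmed at a strict Week 24 cut, although the endpoint window could admit it.

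The primary result is a small count, so one responder matters: it is 6.7 percentage points in a cohort of 15. The study is open-label and responses are reviewed as they arise, so a cut chosen after seeing them could in principle be chosen to suit.

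**Working it through.** The plan has no power, target rate or test to reproduce. Its one sample-size sum, 3 × 15 = 45, is right.

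**1. The sentence in Protocol 9.7.** It conflicts with 9.7.1.6.1 and 9.3.3 unless the study ends at the primary cut. The synopsis foresees 24 to 36 months from first consent to last subject last visit, and follow-up is open-ended only unless the sponsor terminates the study, so the two are closer than they look. Exempting the primary analysis from the sentence would change no subject's response status, no denominator and no interval.

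**2. The trigger read literally.** The inputs are the adult eribulin results in Protocol 7.1.3.2: 12-week progression-free rates from 31.3% to 60.0%, and a median PFS of 2.9 months. The assumptions are exponential PFS and that adult rates apply to children.

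- 24-week rate = (12-week rate)²: 0.313² = 0.098 and 0.600² = 0.360.
- From the median, with 24 weeks = 5.52 months: 0.5^(5.52/2.9) = 0.267.
- Expected at Week 24 without progression, of 15: 15 × 0.098 = 1.5 up to 15 × 0.360 = 5.4.
- P(13 or more of 15) at 0.360 = 0.00008, and less at the lower rates.
- If the 15 were out of all 45, the expected number is 4.4 to 16.2, and P(15 or more) at 0.360 is 0.70.

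These figures show that the literal per-cohort reading is unworkable, which is a reason not to adopt it. On the ordinary reading, a subject is complete at Week 24 or when tumor assessment ends earlier, and the trigger is always reached. On either reading the result is k/n, with n all treated subjects in the cohort and missing status counted as non-response.

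**3. Pending confirmation.** Scans fall at Weeks 6, 12, 18 and 24.

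| First response | Earliest confirmation | Next scheduled scan |
|---|---|---|
| Week 6 | Week 10 | Week 12 |
| Week 12 | Week 16 | Week 18 |
| Week 18 | Week 22 | Week 24 |
| Week 24 | Week 28 | Week 33 if 9-weekly |

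Only the last row runs past Week 24, by 4 to 9 weeks. It matters only for a subject enrolled within that time of the cohort's last subject. The documents give no accrual rate, so assume even accrual of 15 subjects over T weeks, with spacing T/14 and the last subject included:

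| T (weeks) | Spacing (weeks) | Exposed, 4-week wait | Exposed, 9-week wait |
|---|---|---|---|
| 26 | 1.86 | 3 | 5 |
| 52 | 3.71 | 2 | 3 |
| 104 | 7.43 | 1 | 2 |

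Take response rates of 8% (the protocol's figure for another drug class in Ewing sarcoma) and 25% (assumed), spread evenly over the four scans (also assumed). The chance of a first response at Week 24 is then 0.08/4 = 0.02 to 0.25/4 = 0.0625 per subject. Expected affected responders per cohort run from 1 × 0.02 = 0.02 to 5 × 0.0625 = 0.31.

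**4. If it did happen.** Exact (Clopper-Pearson) 95% intervals for n = 15:

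- 0/15: 0%, interval 0 to 21.8%
- 1/15: 6.7%, interval 0.2 to 31.9%
- 2/15: 13.3%, interval 1.7 to 40.5%

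Neighboring counts have heavily overlapping intervals, and the plan sets no numerical bar for one responder to cross.

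**The case for a change.** The strongest case for a change is that this is an open-label go/no-go study with a small count as its result, and neither document dates the data cutoff. SAP 5.4.1 gives none, and the OS and PFS censoring rules refer to a cutoff that is not dated either. A cut fixed after responses are known would be a data-dependent choice, and a few clarifying words would cost little.

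Part of this stands. The wording of Protocol 9.7 is inconsistent with 9.7.1.6.1 and 9.3.3, the per-cohort meaning has to be inferred, and the protocol sentence taken as a strict cut-off would leave a Week 24 response unconfirmed.

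The risk is nonetheless bounded. Only confirmed responses count, so an unconfirmed one is already a non-response without any new rule. The SAP carries the endpoint window and omits the 24-week trigger, so the document that governs the analysis leaves room for a confirmatory scan 4 to 9 weeks later. The longer interval is not forced either, because the move to 9-weekly imaging is optional. Whoever judges whether responses are sufficient will know of a response awaiting confirmation.

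A fixed window ending at each subject's own Week 24 would be tidier, but it would change the endpoint. A numerical responder bar would be a different decision rule and would not correct an error in timing.

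**Conclusion.** No change is called for. The clash with Protocol 9.7 is a clerical slip in a general sentence. The silence on early leavers is a gap that analysts fill in one sensible way, and the Full Analysis Set and SAP 5.3.5 already fix how those subjects are counted. The confirmation question is narrow: about 0.02 to 0.31 responders per cohort, under even accrual over 26 to 104 weeks, response rates of 8% to 25%, and first responses spread evenly over four scans. If one such response did occur, it would move the rate by 6.7 points, but the endpoint window allows it to be confirmed and counted.

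The conclusion rests on reading the 15 subjects as per cohort and on treating an earlier end of tumor assessment as completion. It does not rest on the adult progression-free rates, which only illustrate why the literal reading cannot be meant. No figure stated in the plan is wrong.
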